4.7.1. Primary Efficacy Variable

The primary endpoint is the percent lowering of TG levels from baseline following 12 weeks of repeated IV doses of evinacumab in the subset of patients with a documented history of sHTG (TG >1000 mg/dL [11.3 mmol/L]), a TG level of at least 500 mg/dL (5.6 mmol/L) at screening, a history of acute pancreatitis, and without LOF mutations in genes in the LPL pathway.

Only fasting TG measurements will be included in the analysis. TG measurements with missing fasting status will be excluded from the analyses.

4.7.2. Lipids Variables

Potential clinical benefits of study treatment will be explored through the following lipids parameters: LDL-C (Ultracentrifugation), HDL-C, total-C, fasting TG, non-HDL-C, Apo B, Apo A1, Apo CIII, Apo B/Apo A1 ratio, and Lp(a).

Baseline TG is defined as the mean of the last 2 measurements during the placebo run-in (day -28, day -14) and week 0.

Lipids parameters will be collected in a fasted state over the course of the study at time points listed in [Appendix 10.4](#), and sent to the central laboratory for evaluation, including scheduled and unscheduled blood draws. Both the absolute change from baseline and the percent change from baseline will be calculated for each lipids parameter, and derivations will be presented in

both international and conventional units. TG measurements with missing fasting status will be excluded from the summaries.

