The single-blind placebo run-in period allows for measurement of change from baseline in TG in patients randomized to placebo. The double-blind period allows for an unbiased assessment of the safety of evinacumab compared to placebo. The single-blind period allows for analysis of a treatment effect in patients randomized to placebo. A single-blind period is preferred over an open-label period to allow for unbiased collection of patient reported outcomes by the study participants.

Since fasting TG are highly variable in this population, the geometric mean of TG measurements obtained at specific time-points (day -28, day -14 and week 0) will be used for pre-treatment comparison for the 12-week double blind period. For patients receiving placebo during the double-blind treatment period, the geometric mean obtained at specific time points (week 6, 8, and 12) will be used as the baseline measurements for the single-blind evinacumab treatment period. A placebo controlled double-blind period will allow an unbiased assessment of safety of evinacumab versus placebo. Furthermore, offset kinetics will be observed in patients following withdrawal of active study medication.

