To reduce variability of TG baseline measurements, baseline at week 0 for patients randomized to active treatment is the geometric mean of the last 2 measurements during the placebo run-in (day -28, day -14) and week 0. Baseline at week 12 for patients switching from placebo to active is the geometric mean of the last 2 measurements during the placebo phase (weeks 6, 8) and first measurement prior to active infusion (week 12). Additional exploratory analyses may be carried out using the average of all available TG observations prior to first dose of active treatment, if no trend over time in those measurements is discernable.

Using the estimate of the log TG mean ratio (week 12/baseline at week 0 for patients randomized to evinacumab and week 24/baseline at week 12 for those randomized to placebo) and the log of the standard deviation derived from the MMRM model, the PP will be calculated using the target percent change from baseline of 40% reduction (ie, log 0.6) in patients without LOF mutations in genes in the LPL pathway. For the probability calculation (ie, $\text{Pr} [\log \text{TG mean ratio (post/pre)}] < \log 0.6$ conditional on this study's TG results), a non-informative normal distribution prior and a normal distribution of the data is assumed. The probability calculation will yield the probability that the actual mean percent decrease is at least the target 40% value, based on the OBSERVED results from the patients without LOF mutations in genes in the LPL pathway.

This fixed sequence design assumes no carryover effect from the placebo run-in period into the active treatment period. This assumption will be verified by assessment of the time course of TG observations during the run-in period. A generally flat or non-decreasing trend over time in the placebo run-in period will be evidence of no carryover effect into the active treatment period and of a useful valid baseline benchmark against which to compare treatment effects based on within-patient comparisons (active treatment period to placebo run-in period). As a sensitivity analysis, the TG reduction and posterior probability analyses of the combined sequence groups will be repeated using the same baseline at week 0. Note that the follow-up period is expected to have

carryover effects from the active treatment period and is included to estimate the time course of those effects. Such carryover effects may also be interpreted as evidence of treatment effects.

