	
analysis.”
 
“To reduce variability of TG baseline measurements, baseline at week 0 for patients randomized to active treatment is the geometric mean of the last 2 measurements during the placebo run-in (day -28, day -14) and week 0.”
	mean (arithmetic), since the log-transformed geometric mean of measurements is equivalent to the arithmetic mean of log-transformed measurements.
5	10.4.3.2 Secondary and Exploratory Efficacy Analysis	
SAP Section 5.7.2, 5.9 to 5.12:
 
Analyses for each secondary and exploratory endpoint are specified in the corresponding sections for each endpoint.The statement that “Continuous secondary and exploratory endpoints will be analyzed similarly to the primary endpoint” was deleted since for some continuous variables MMRM model may not converge due to the small number of visits/observations
6	10.4.5.3 Treatment Exposure The duration of exposure during the study will be presented and calculated as: (Date of last evinacumab injection - date of first evinacumab injection) + 24 weeks (length of follow-up period)	
SAP Section 4.6:
 
Duration of exposure was divided to double-blind and single-blind period and the duration definition was changed to “...+28 days/7” to be consistent with other evinacumab studies.

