5.7.1. Analysis of Primary Efficacy Variable

The primary efficacy analysis will assess within-patient percent change in TG over 12 weeks of evinacumab treatment (double-blind period for patients randomized to evinacumab and single-blind period for patients randomized to placebo).

The point estimates of TG percent changes between the placebo period and each observation week will be calculated using a Mixed-effect Model for Repeated Measures (MMRM) method in the FAS population. A natural log transformation will be applied to the TG levels prior to

analysis, aiming to provide a relatively normal data distribution (residuals will be examined for normality prior to proceeding with the analysis). The MMRM model will assess within-patient treatment comparisons (using an unstructured covariance matrix), while accounting for baseline TG, study visit, and baseline TG by study visit interaction. Note that study visits will be adjusted to start of evinacumab in order to pool data from both randomized groups of patients for this analysis. Since the comparison of study visits yields the within-patient comparisons of study treatments (ie, week 12 [after 12 weeks of treatment with evinacumab] compared to baseline at week 0 [after 4 weeks of treatment with placebo] for patients randomized to evinacumab and week 24 [after 12 weeks of treatment with evinacumab] compared to baseline at week 12 for those randomized to placebo), contrast and estimate statements will be used to assess treatment effects (least squares [LS] means with confidence intervals) and comparisons (LS mean ratio with CI). Within-patient comparisons will include all patients. In the event the MMRM model covariance matrix does not converge or normality is not achieved with the natural log transformation, then other transformations will be explored, including ranks.

To reduce variability of TG baseline measurements, baseline at week 0 for patients randomized to active treatment is the mean of the 3 log-transformed measurements at day -28, day -14, and week 0. Baseline at week 12 for patients switching from placebo to active is the mean of 3 log-transformed measurements at weeks 6, 8, and 12. Additional exploratory analyses may be carried out using the average of all available TG observations prior to first dose of active treatment, if no trend over time in those measurements is discernable.

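### SAP 4.1 and 4.7.2 leave baseline TG as an unqualified (by SAP 1.2.4, arithmetic) mean where the protocol and the primary model use a geometric mean, shifting descriptive median TG changes towards a reduction

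*SAP*

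**What the plan says.** The protocol defines the week 0 baseline geometrically in two places. Section 3.2.1, citing the high variability of fasting TG in this population, says that "the geometric mean of TG measurements obtained at specific time-points (day -28, day -14 and week 0) will be used for pre-treatment comparison". Section 10.4.3.1 says that "baseline at week 0 for patients randomized to active treatment is the geometric mean of the last 2 measurements during the placebo run-in", together with the week 0 value.

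SAP 5.7.1 keeps that quantity on the log scale for the primary model: the week 0 baseline "is the mean of the 3 log-transformed measurements at day -28, day -14, and week 0".

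SAP 4.1 and 4.7.2 use the protocol's sentence without the word geometric: "Baseline TG is defined as the mean of the last 2 measurements during the placebo run-in (day -28, day -14) and week 0". Neither section mentions a log transformation. SAP 1.2.4, item 4, records the change as one to the "mean (arithmetic), since the log-transformed geometric mean of measurements is equivalent to the arithmetic mean of log-transformed measurements".

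SAP 4.7.2 then applies its baseline to raw-scale results: "Both the absolute change from baseline and the percent change from baseline will be calculated for each lipids parameter". SAP 5.7.2 reports these by visit, treatment group and cohort, and plots TG change as medians with quartiles. SAP section 7 limits lipid results at the cohort 1 interim (9 patients) to descriptive summaries.

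**The concern.** The identity in SAP 1.2.4 is correct: the log of a geometric mean equals the mean of the logs. It justifies the 5.7.1 baseline, which enters the model on the log scale. It does not justify averaging raw mg/dL values in 4.1 and 4.7.2, because there the arithmetic and geometric means are different numbers. They differ most when TG varies a lot within a patient, which is the protocol's own reason for choosing the geometric mean.

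A programmer who reads 4.7.2 together with 1.2.4 would average raw values. Each post-baseline visit is a single measurement, so its median is compared with a baseline that sits above the patient's typical level. The TG plots, and any medians in the TG tables, would then show some lowering when nothing has changed, and would not agree with the primary model. The cohort 1 interim has only descriptive lipid output and is meant to inform later development. Protocol section 1 reports that some patients with LPL and other mutations did not show robust lowering, so a few points of apparent reduction could be misread there.

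**Working it through.** **Inputs from the documents.** Log-scale SD of TG change 0.5 (SAP 2.2, protocol 10.2); target reduction 40%, a ratio of 0.6; three baseline values and one value per follow-up visit.

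**Assumed input.** The documents give no within-patient log SD, called s here, so a range is used.

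**1. The plan's own precision figure.** The 90% limits for the reduction are 1 − 0.6 × exp(±t × 0.5/√N).
- N = 10: t = 1.833, half-width 1.833 × 0.5/√10 = 0.290, limits 19.8% and 55.1%. The plan states 20% to 55%.
- N = 12: t = 1.796, half-width 0.259, limits 22.2% and 53.7%. The plan states 22% to 54%.

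Both reproduce, so 0.5 is the SD of log(post/baseline).

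**2. Upper limit for s.** With a baseline that averages three logged values and one follow-up value, measurement variation alone gives variance s² + s²/3 = (4/3)s². Setting (4/3)s² = 0.25 gives s = 0.433. A larger s would exceed the plan's SD of 0.5 before any variation in treatment response.

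**3. Direction for one patient.** Let AM and GM be the arithmetic and geometric means. Then post/AM = (post/GM) × (GM/AM), and GM/AM ≤ 1. If the reduction from the GM is exactly 40%:

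| Baseline values (mg/dL) | AM | GM | Reduction from AM |
|---|---|---|---|
| 1000, 1000, 1000 | 1000 | 1000 | 40.0% |
| 800, 1000, 1250 | 1016.7 | 1000 | 1 − 600/1016.7 = 41.0% |
| 1000, 2000, 3000 | 2000 | 1817.1 | 1 − 0.6 × 1817.1/2000 = 45.5% |

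**4. Size across patients.** For three lognormal values GM/AM is about exp(−s²/3). At s = 0.3 this is exp(−0.03) = 0.970, and 1 − 0.6 × 0.970 = 41.8%. Simulation with at least 1,000,000 patients per scenario gives these medians:

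| s | No true effect, AM baseline | 40% reduction, AM baseline |
|---|---|---|
| 0.2 | −1.3% | 40.8% |
| 0.3 | −2.9% | 41.7% |
| 0.4 | −5.0% | 43.0% |
| 0.433 | −5.9% | 43.5% |

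The GM baseline gives 0% (within 0.1 point) and 40% throughout.

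**5. Arithmetic means of change.** These behave differently. With no true effect, the mean percent change from a GM baseline is exp(2s²/3) − 1. At s = 0.3 this is exp(0.06) − 1 = +6.2%; simulation with the AM baseline gives +3.1%. Mean absolute change is zero with the AM baseline. With the GM baseline it is exp(s²/2) − exp(s²/6) = 1.046 − 1.015 = +3.1% of the patient's typical (median) TG at s = 0.3.

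**6. Placebo patients in the single-blind period.** The protocol's baseline for them is the geometric mean of weeks 6, 8 and 12. With no drift, the run-in AM exceeds that value in 53.2%, 54.8% and 56.7% of patients at s = 0.2, 0.3 and 0.433. The direction is therefore not fixed.

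**The case against.** The best defence has four parts.

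- **Wording.** SAP 4.1 and 4.7.2 never say arithmetic, and SAP 1.2.4 offers its change as a clarification that refers to logged values. It may be incomplete shorthand. That is possible, but 1.2.4 does use the word arithmetic, and 5.7.1 shows that the SAP says log-transformed when it means it. At the least, two baselines are open to the programmer.
- **The arithmetic baseline suits some summaries.** It leaves mean absolute change unbiased and brings mean percent change closer to zero (+3.1% against +6.2% at s = 0.3 with no effect). This stands. A reader might infer that every descriptive TG reduction is inflated, or that a geometric baseline costs nothing. The documents support neither: the effect concerns medians, and it vanishes when a patient's three values are equal.
- **Size.** Larger shifts follow only from s above 0.433, which conflicts with the plan's SD of 0.5. This stands, and the range is capped accordingly.
- **Consequence.** The MMRM reviewed against a 40% reduction uses logged baselines, and the p-values in 5.7.2 are labelled descriptive. This also stands. It limits the weight of the point but does not reconcile the definitions.

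**Conclusion.** The inconsistency holds, with a modest effect confined to descriptive results. Read with SAP 1.2.4, sections 4.1 and 4.7.2 depart from protocol 3.2.1 and 10.4.3.1 and from SAP 5.7.1, on a justification that does not extend to raw values. Median TG changes from the run-in baseline move towards a reduction by about 1 to 6 points with no true effect, and by about 1 to 3.5 points at a 40% reduction.

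These sizes assume lognormal, independent measurements without drift and s between 0.2 and 0.433; only the upper end is tied to a figure in the documents. The outputs affected are the TG plots and any medians in the TG summaries, including the cohort 1 interim. It would be wrong to conclude that the primary result is biased, or that the single-blind summaries for placebo patients are shifted in a known direction.

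**What to change.** 1. In SAP 4.1 and 4.7.2, define baseline TG as the geometric mean of the day -28, day -14 and week 0 values, that is, the exponential of the mean of their logs.
2. In SAP 1.2.4, item 4, limit the equivalence argument to the log-scale model and remove the implication that the raw-scale baseline becomes arithmetic.
3. In SAP 5.7.2, and for the interim in section 7, summarise TG change by medians or geometric mean ratios.

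The cost is a few sentences and no new data. There is one small downside. With a geometric baseline, arithmetic means of raw percent and absolute change are shifted upward, at s = 0.3 by about 3 points compared with the arithmetic baseline. If those means are still tabulated, they should carry a note and should not be the headline TG summary.

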4.7.3. Other Variables

Other assessment endpoints are listed and defined below.

- The change in hemoglobin A1c (HbA1c [%]) from baseline to post-baseline visits.
- The percent change in hs-CRP from baseline over time
- Post heparin LPL activity
- Apolipoproteins: APOC2, APOA5
- Metabolic parameters (fasting blood glucose, insulin, C-peptide, NEFA)

4.7.4. PET Variable(s)

The F-FDG PET endpoints are listed below:

- Percent change in pancreatic 18F-FDG standardized uptake values SUVmax and SUVmean from baseline at week 12
- Percent change in 18F-FDG-PET target to background ratio [TBR] in carotids and/or aorta atherosclerotic plaques at week 12
- The change in pancreatic ¹⁸F-FDG Ki or Kpatlak from baseline at week 12

4.7.5. MRI Variable(s)

The MRI endpoints are listed below:

- The change in apparent diffusion coefficient (ADC) in the pancreas from baseline to post-baseline visits
- The change in T2 signal in the pancreas from baseline to post-baseline visits
- The change in hepatic fat fraction from baseline to post-baseline visits

The baseline value is defined as the mean of two measurements prior to the date of the first double-blind study treatment administration (applicable to measurement derivations during both DBTP and SBTP)

4.8. Safety Variables

Patient safety will be assessed through the collection of reported adverse events (AEs), clinical laboratory data, vital signs, and ECG. Unless otherwise noted, the baseline value is defined as the last available value before the first dose of double-blind study treatment.

4.8.1. Adverse Events Variables

The period of safety observation starts from the time when the patient gives informed consent and continues into the following periods:

- The PRE-TREATMENT period is defined from the day the ICF is signed to the day before the first dose of double-blind study treatment administration.
- The double-blind treatment-emergent adverse event (TEAE) period is defined from the day of the first dose of double-blind study treatment administration to the day of the last dose of double-blind study treatment administration + 168 days (24 weeks) for those patients not proceeding into the SBTP, or up to the day before the first dose of single-blind study treatment administration for those patients proceeding into the SBTP.
- The single-blind treatment-emergent adverse event (TEAE) period is defined from the day of the first single-blind study treatment administration to the day of the last single-blind study treatment administration + 168 days (24 weeks).
- The POST-TREATMENT period is defined from the day after the end of the respective TEAE periods to the last study visit.

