5. STUDY DESIGN

5.1. Study Description and Duration

This is a phase 2, randomized, placebo-controlled, study designed to evaluate the efficacy and safety of repeated doses of evinacumab in adult patients with severe HTG. Up to approximately 50 patients will be enrolled, randomized 2:1 (evinacumab:placebo) to receive evinacumab or placebo.

[figure not shown]
The study consists of a screening period of up to 37 days (which includes day -66 to day -59 [visit 1], day -58 to -52 [visit 1b], and day -51 to -39 [visit 2]), a baseline/single-blind placebo run in period (day -28 to day -1), a 12-week double-blind treatment period (day 1 to day 85), a single-blind 12-week treatment period (day 86 to day 169), and an off-treatment follow-up period (week 24 [day 170] to week 44 [day 309]).

The following cohorts will be enrolled based upon information (or lack of information) on genotype in the patient's medical history at screening:

1. Cohort 1: FCS due to complete LPL deficiency. Approximately 6 to 9 patients will be enrolled. This cohort consists of patients:
 - with known homozygous or compound heterozygous null LPL, GPIHBP1, or APOC2 LOF mutations
2. Cohort 2: Multifactorial chylomicronemia with partial LPL deficiency. Approximately 9 to 12 patients will be enrolled. This cohort consists of patients:
 - with known heterozygous null LPL, GPIHBP1, or APOC2 LOF mutations, or
 - with uncharacterized or known non-null LOF LPL pathway gene mutations (LPL, apoC2, apoA5, LMF1 and GPIHBP1)
3. Cohort 3: Multifactorial chylomicronemia. Approximately 15 to 27 patients will be enrolled. This cohort consists of patients not included in cohorts 1 or 2 above:
 - with other monogenic or polygenic causes of sHTG (eg, CGKR, CREB3L3, E2/E2 dysbetalipoproteinemia), or
 - without genotype information

A study flow diagram is in [Figure 1](#).

Figure 1: Study Flow Diagram

Screening (Day -66 to Day -29)

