2.3. Study Plan

The study consists of a screening period of up to 37 days (which includes day -66 to day -59 [visit 1], day -58 to -52 [visit 1b], and day -51 to -39 [visit 2]), a placebo run-in period (day -28 to day -1), a 12-week double-blind treatment period (day 1 to day 85), a single-blind 12-week evinacumab treatment period (day 86 to day 169), and an off-treatment follow-up period (week 24 [day 170] to week 44 [day 309]).

A study flow diagram is in [Figure 1](#).

Figure 1: Study Flow Diagram

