5.7.3. Analysis of Other Variables

Descriptive statistical analyses for other endpoints (described in Section 4.7.3) will be summarized by treatment group and overall for the study, as well as by treatment group and overall in the FAS population. For summary tables, only protocol scheduled measurements (as defined by e-CRF visit label) will be included. Patient listings will include all measurements, scheduled and unscheduled.

The summary of results for other variables will be presented separately for the DBTP and SBTP, unless otherwise noted. Summaries for the DBTP will be presented by treatment groups

(evinacumab, placebo) containing patients from the double-blind safety analysis set. Summaries for the SBTP will be presented by all patients and by treatment group in DBTP (i.e., evinacumab, placebo), for patients in the single-blind safety analysis set. No formal inferential testing will be performed for either period. Summaries will be descriptive in nature.

Hs-CRP and HbA1c parameters will be summarized at each protocol-scheduled visit. The medians (with Q1-Q3) will be plotted for hs-CRP and HbA1c. Applying the PCSV criteria at any time during the TEAE period, the number of patients (and percentages) meeting the criteria will be summarized.

Similar tables, except PCSV criteria, will be provided for post heparin LPL activity, APOC2, APOA5, and metabolic parameters.

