5.8.7. Analysis of 12-Lead ECG

For respective treatment period (DBTP and SBTP), ECG parameters will be described through an overall interpretation of ECG status (e.g. normal, abnormal [clinically significant (Yes/No)]). The count and percentage of patients with at least 1 abnormal post-baseline ECG during the respective TEAE period will be summarized according to the following baseline status categories:

- Normal/missing;
- Abnormal

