10.4.1. Footnotes for the Schedule of Events Table

1. Patients who are permanently withdrawn from study drug before entering the double-blind treatment period (day 1, week 0) will be contacted to assess any AEs.
2. Patients who are permanently withdrawn from the study drug during double-blind period will be asked to return to the clinic for an early termination visit consisting of week 12 study assessments. After the early termination visit, patients will enter the off-drug treatment follow-up period.
3. Patients who are permanently withdrawn from study drug during the single-blind treatment period will be asked to return to the clinic for an early termination visit consisting of week 24 study assessments. After the early termination visit, patients will enter the off-drug treatment follow-up period.
4. Visit 1b must occur at least 4 days after visit 1.
5. Patients will undergo end of double-blind treatment period assessments at the week 12 visit, which is the first visit of administration of single-blind evinacumab.
6. Medical history should include detailed cardiovascular and pancreatitis history.
7. The patient should be fasting for at least 8 hours prior to the post-heparin procedure for measurement of LPL activity. The patient should not consume any alcohol 48 hours prior to the post-heparin plasma blood draw. Heparin (60 U/kg body weight) should be administered IV by bolus injection. Venous blood should be collected 10 minutes after the bolus injection. Prior to discharge from the clinic, patients should then be observed for 1 hour post-heparin administration for any AEs.
8. Following the screening period and confirmation of eligibility, patients will receive an IV bolus of 60 IU of heparin per kg of body weight at visit 2.
9. At dosing visits, all assessments (including urine or serum pregnancy tests for WOCBP) should be performed and all blood samples should be collected before the dose of study drug is administered.
10. Vital signs should also be measured and AEs monitored pre-dose, at the end of study drug infusion, between 30 to 60 minutes post dose, and at approximately 120 minutes post dose. Patients will be closely monitored for a minimum of 120 minutes after IV administration of study drug.
11. Patients should fast for a minimum of 8 hours prior to all blood draws. For patients with diabetes, investigators may hold a patient's morning diabetes medications until labs are drawn and the patient has eaten.

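### The date rule in SAP 4.8.1 moves pre-dose week-12 safety assessments into the single-blind period, so the double-blind ECG, HbA1c, hs-CRP and urine pH outputs have no scheduled data for patients who continue

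*SAP*

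**What the plan says.** SAP 4.8.1 defines two TEAE periods. For a patient who continues, the double-blind period runs "up to the day before the first dose of single-blind study treatment administration for those patients proceeding into the SBTP". The single-blind period starts on the day of that dose and ends 168 days after the last single-blind dose. Nothing divides the day of the first single-blind dose at the time of infusion. Protocol 10.4.5.1 also ends its double-blind safety period on the day before.

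The study plan draws the line one day later. SAP 2.3 has "a 12-week double-blind treatment period (day 1 to day 85), a single-blind 12-week evinacumab treatment period (day 86 to day 169", and Protocol 5.1 has "a 12-week double-blind treatment period (day 1 to day 85), a single-blind 12-week treatment period (day 86 to day 169". Protocol 7.1 gives the single-blind infusions on days 85, 113 and 141.

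Footnote 5 to the SAP schedule (10.4.1) says what the week-12 visit is for: "Patients will undergo end of double-blind treatment period assessments at the week 12 visit, which is the first visit of administration of single-blind evinacumab". Footnote 9 says that at dosing visits "all blood samples should be collected before the dose of study drug is administered", and footnote 17 puts the ECG before the blood draw.

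Several outputs are tied to the TEAE period:
- SAP 5.8.7 counts patients with "at least 1 abnormal post-baseline ECG during the respective TEAE period".
- SAP 5.7.3, for HbA1c and hs-CRP, says: "Applying the PCSV criteria at any time during the TEAE period, the number of patients (and percentages) meeting the criteria will be summarized".
- SAP 5.8 and 5.8.5 count PCSVs and draw the eDISH plot within the respective TEAE periods.
- The HbA1c rule for new-onset diabetes in SAP 10.2 refers to the TEAE period.

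Under SAP 4.8, "the baseline value is defined as the last available value before the first dose of double-blind study treatment", and this holds for both periods.

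**The concern.** The week-12 ECG and blood samples describe the patient at the end of randomized treatment, before any single-blind evinacumab. A rule based on calendar date alone files them under the single-blind period, because they carry the date of the first single-blind infusion. Baseline remains the value before the double-blind period, so such a result does not become a new baseline. It counts as a post-baseline single-blind finding.

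The double-blind period is the only placebo-controlled part of the study, and Protocol 3.2.1 presents it as the source of the unbiased safety comparison. For tests done only at week 12 within that period, the comparison would lose its only scheduled post-baseline record in every continuing patient. The PCSV denominator in SAP 5.8 is patients assessed at least once in the period. For HbA1c, hs-CRP and urine pH it would shrink to patients who did not continue, plus anyone with an unscheduled value, and that is a selected group. Abnormalities that arose on placebo would enter the pooled single-blind column, and a new-onset-diabetes case could change period or disappear.

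**Working it through.** **Inputs**
- Double-blind infusions on days 1, 29 and 57; single-blind infusions on days 85, 113 and 141 (Protocol 7.1).
- TEAE period definitions (SAP 4.8.1).
- Scheduled tests (Protocol Table 1, SAP 10.4). After the first double-blind dose, ECG, HbA1c, hs-CRP and urinalysis fall at weeks 12, 24 and 44. Chemistry and hematology fall at weeks 2, 4, 6, 8, 12, 16, 20, 24, 28, 36 and 44.
- Up to about 50 patients, randomized 2:1 (SAP 2.1).

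The plan gives no figure of its own to reproduce on this point.

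**Step 1: periods on the nominal schedule**
- Double-blind TEAE period: day 1 to day 85 − 1 = day 84.
- Single-blind TEAE period: day 85 to day 141 + 168 = day 309 (week 44).
- SAP 2.3: double-blind to day 85, single-blind from day 86.

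Week 12 (day 85) is therefore single-blind under SAP 4.8.1 and double-blind under SAP 2.3.

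**Step 2: scheduled post-baseline records per continuing patient**

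| Test | Double-blind, date rule | Double-blind, visit label | Single-blind, date rule | Single-blind, visit label |
|---|---|---|---|---|
| ECG, HbA1c, hs-CRP, urinalysis | 0 | 1 | 3 | 2 |
| Chemistry, hematology | 4 | 5 | 7 | 6 |

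**Step 3: HbA1c rule for new-onset diabetes**

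SAP 10.2 flags a patient with two or more values of at least 6.5%, with only the last of several at that level, or with a single available value at that level. I applied it separately within each period, assuming all three scheduled values and no unscheduled HbA1c. There are 2³ = 8 patterns (1 = at least 6.5%, in the order weeks 12, 24, 44).

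| Pattern | Date rule | Visit label |
|---|---|---|
| 000 | none | none |
| 001 | single-blind | single-blind |
| 010 | none | none |
| 011 | single-blind | single-blind |
| 100 | none | double-blind |
| 101 | single-blind | double-blind and single-blind |
| 110 | single-blind | double-blind |
| 111 | single-blind | double-blind and single-blind |

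The date rule gives a double-blind flag in 0 of 8 patterns and the visit label in 4 of 8. All four patterns with a high week-12 value lose the double-blind flag. Pattern 100 is then flagged in neither period, and pattern 110 moves to the single-blind period alone.

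**Step 4: placebo patients with reassigned records**

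50 / 3 = 16.7, so at most about 17.

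**Step 5: outputs that are not affected**

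The by-visit HbA1c and hs-CRP tables (SAP 5.7.3) keep week 12. By-visit laboratory and vital-sign tables run to last dose + 28 days (SAP 5.8.5, 5.8.6). Nominally 57 + 28 = day 85, so they also keep week 12, although a visit held more than 28 days after the last double-blind dose would drop out. The same week-12 chemistry value can therefore be double-blind in the by-visit table and single-blind in the PCSV table.

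**The case against.** The best reply is that this is an ambiguity and not a misassignment. No sentence says outright that pre-dose week-12 records are single-blind. Footnote 5 calls them end-of-double-blind assessments, and SAP 5.8 limits summary tables to measurements carrying a scheduled visit label. That does not settle it: the label decides which measurements enter a summary table, while the ECG and PCSV counts are assigned by TEAE period.

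A second reply is that the day 85/86 text is only a nominal description. The analysis definitions agree with one another: SAP 4.8.1, Protocol 10.4.5.1 and the concomitant-medication periods in SAP 4.3. It is true that SAP 4.8.1 does not depart from the protocol's safety section, and the date rule is reasonable for adverse-event onset. The conflict with footnote 5 and with the purpose of the week-12 visit remains.

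Three points limit the size:
- The diabetes counts depend on applying the rule within each period. SAP 10.2 does not say so explicitly. Over the whole post-dose span, moving week 12 would change no flag. Presentation by period is, however, the stated default for safety in SAP 5.8. The separate fasting-glucose criterion keeps its weeks 2 to 8 values in the double-blind period.
- Both arms lose the same record, so information is lost but no directional bias between arms is shown.
- Safety analysis is descriptive, and single-blind tables also show the former-placebo group. Moved events can be traced, but they still carry the wrong period label and the controlled comparison is still missing.

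**Conclusion.** The concern holds. Followed as written, SAP 4.8.1 leaves the double-blind ECG abnormality table, the HbA1c, hs-CRP and urine pH PCSV counts and the HbA1c diabetes rule with no scheduled post-baseline record for any patient who continues. Results obtained at the end of placebo treatment are labelled single-blind. Chemistry and hematology PCSVs and eDISH lose one of five scheduled double-blind records. By-visit tables are nominally intact, and no efficacy endpoint is involved.

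This rests on assessments being done on the date of the first single-blind infusion. An assessment on an earlier date stays double-blind. Patients who do not continue keep their records in the double-blind period, which for them runs to last dose + 168 days. The single-blind count of 3 is nominal, because the week-44 visit has a window of ±5 days around a period that ends on day 309. Unscheduled values may leave some double-blind data. The number of abnormal week-12 results cannot be known from the documents.

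**What to change.** Add to SAP 4.8.1 that assessments performed pre-dose at the week-12 visit, identified by e-CRF visit label and planned pre-dose time point, belong to the double-blind period for the ECG, PCSV, eDISH and new-onset-diabetes analyses. For these outputs the single-blind period then starts at the first single-blind infusion. Post-infusion vital signs and infusion reactions on that day remain single-blind. State in SAP 10.2 that the HbA1c rule is applied within each period, if that is intended.

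Align Protocol 10.4.5.1 with a matching line. If an amendment is not wanted for this alone (Protocol 15 requires IRB/EC approval), record the difference in the modifications table of SAP 1.2.4. Reconcile the day 85/86 boundary in SAP 2.3 and Protocol 5.1 with the rule adopted.

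The cost is one or two sentences in the SAP plus the matching protocol line or table entry. No new data and no assessment clock times are needed.
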